31.0 AMENDMENT 7: SUMMARY OF CHANGES

31.1 Introduction:

Amendment 7 consists of administrative changes to the table of contents and sections 15.1 and 15.2.

31.2 Rationale:

To correct errors and add missing CSF secondary endpoint.

32.0 AMENDMENT 8: SUMMARY OF CHANGES**32.1 Introduction:**

In section 15.2 we stated "Participants will also be classified as early MCI (EMCI) if baseline CDR-SB is less than 1.5, and late MCI (LMCI) if CDR-SB is greater than 1.5." This doesn't say what happens if a patient falls at 1.5. Amendment 8 revises to state LMCI as 1.5 or greater.

32.2 Rationale:

The 1.5 cut-off more accurately depicts the early and late MCI status in that there are no conversions at year 1, and only 1 conversion at year 2 in the early MCI status.

33.0 AMENDMENT 9: SUMMARY OF CHANGES**33.1 Change:**

The protocol is amended to include unblinding subjects who want to know if they received IVIG or placebo. Subjects participating in the extension portion of the study may be unblinded upon study completion. Subjects who declined participation in the extension portion of the study or who did not complete the study will be unblinded upon request.

The Principal Investigator will inform subjects of their group assignment at their last study visit, and will not have access to individual subject data following study completion.

This unblinding protocol was approved by the DSMC on 6/3/16. No changes were made to the unblinding protocol during study participation.

33.2 Rationale:

There are current and future studies for MCI and AD that exclude subjects who have had prior immunotherapy. If subjects remain blinded, placebo arm subjects will not have a chance to participate in these trials.

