6.5 Blinding and unblinding

The study coordinator, investigator, and infusion nurse will be blinded to whether the subject is receiving placebo or NewGam. The pharmacist will receive the assignment from the research scientist who will develop the randomization scheme. Both will know of the subject's treatment assignment. While participating in the study, a subject's treatment assignment should only be unblinded when knowledge of the treatment is essential for the further medical management of the subject. Unblinding for any other reason during the study will be considered a protocol violation.

Subjects participating in the extension portion of the study may be unblinded upon study completion (Visit 15/month 60). Subjects declining participation in the extension portion of the study or subjects not completing the study will be unblinded upon request.

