9.2 Replacement of subjects

Subjects screened but not randomized will be replaced. Subjects withdrawn after receiving the third infusion will not be replaced but will be followed if they provide consent.

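### Amendment 9 has the blinded Principal Investigator disclose assignments at a visit that also collects endpoints, with no rule on order and no wait for subjects still in blinded follow-up

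*Combined protocol and SAP*

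**What the plan says.** Section 6.5 is explicit about who is blinded: "The study coordinator, investigator, and infusion nurse will be blinded to whether the subject is receiving placebo or NewGam". The pharmacist and the research scientist know the assignments. Apart from medical need, the section treats unblinding during a subject's participation as a protocol violation.

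The same section then sets out when subjects may be told. For the extension: "Subjects participating in the extension portion of the study may be unblinded upon study completion (Visit 15/month 60"). For the rest, those who decline the extension and "subjects not completing the study will be unblinded upon request".

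Section 33.1 (Amendment 9) limits the purpose: "The protocol is amended to include unblinding subjects who want to know if they received IVIG or placebo". It also names who does the telling: "The Principal Investigator will inform subjects of their group assignment at their last study visit". The same sentence adds that this person "will not have access to individual subject data following study completion". It records that the monitoring committee approved the arrangement on 6/3/16. The rationale in 33.2 is that other MCI and AD trials exclude people with prior immunotherapy, so placebo subjects who stay blinded would be shut out.

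Amendment 9 is the latest change, so 33.1 is not superseded text. Section 6.5 carries its timing but not the name of the person who discloses.

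**The concern.** The plan asks someone it lists as blinded to deliver assignments one subject at a time, in a single-centre trial where others may still be under observation. Two protections are missing: a rule that the visit's assessments come before disclosure, and a rule that keeps the investigator uninformed until the last subject has finished.

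At stake is the blinded evaluation at 36, 48 and 60 months in section 2.2. CDR, ADAS-Cog and the diagnosis of AD involve judgement by the rater, subject or informant. The investigator also assesses whether adverse events are related to study drug (10.5), may withdraw subjects (9.1), and may approve cognition-enhancing products that are otherwise barred (6.11.1). Someone who has seen a few assignments beside the matching histories can start to link arm with outcome or side effects while those decisions continue.

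**Working it through.** The plan gives no figure on this point to reproduce, so the check sets the sections side by side.

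1. **Does the investigator learn the assignment?** 6.5 says the investigator is blinded; 33.1 says the Principal Investigator informs the subject. No route around this, such as a sealed letter or disclosure by the pharmacist, is described. So yes, for each subject who asks.

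2. **What else happens at the last visit?** Sections 7.9 (Visit 12) and 7.12 (Visit 15) both list the MRI for ventricular volume, MMSE, ADAS-Cog, CDR-SB, examinations and adverse event recording. In Appendix C the Early Termination visit shares those columns. Neither 6.5 nor 33.1 orders assessment and disclosure.

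3. **Are other subjects still being followed?** Section 3.3 counts visits from each subject's first infusion, and neither section makes disclosure wait for other subjects or for database lock. Any staggered entry therefore gives overlap. Enrolment dates are not given, so the following is an illustration only. Assume 50 subjects enter evenly over E months, at e_i = i × E/49 for i = 0 to 49, and all join the extension. When the first reaches month 60, count the others whose own month 60 is more than 28 days away (two 14-day windows; 28/30.4 = 0.92 months), and those whose month 48 is also outstanding (e_i > 60 − 48 = 12).

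| Assumed accrual E (months) | Month 60 outstanding | Month 48 also outstanding |
|---|---|---|
| 6 | 42 | 0 |
| 12 | 46 | 0 |
| 18 | 47 | 17 |
| 24 | 48 | 25 |
| 30 | 48 | 30 |

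 For E = 24 the spacing is 24/49 = 0.49 months. Subjects i = 2 to 49 exceed 0.92 (48 subjects), and i = 25 to 49 exceed 12 (25 subjects). Fewer extension subjects would lower every count. The table shows that overlap is large under any plausible accrual; it does not measure bias.

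4. **Does the data-access limit close the gap?** It begins after study completion. In 6.5 that phrase is tied to a subject's own Visit 15; 33.1 does not say whether it means the subject or the whole study. On either reading it restricts access to records. It does not restrict what the Principal Investigator knows while seeing other subjects.

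5. **Withdrawn subjects.** Under 9.2, subjects withdrawn after the third infusion "will not be replaced but will be followed if they provide consent". Section 6.5 lets non-completers ask for their assignment without saying whether those still followed must wait.

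**The case against.** The strongest reply has five parts.

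- **Natural reading.** Disclosure on completing the study most naturally means after that visit's assessments. A reader might infer that subjects are told while endpoints are being taken, but no section says so. What stands is the missing order.
- **Scope.** A reader might infer that the investigator learns every subject's arm. 33.1 covers only those who want to know.
- **Timing.** A reader might infer that the month-24 comparison is compromised by disclosure at Visit 12. Amendment 8 already cites year-2 conversions, and 33.1 refers in the past tense to subjects who declined. Many month-24 visits had therefore probably taken place before the rule existed. This is not proven, but it moves the weight to months 36 to 60.
- **Information.** Knowing finished subjects' arms says little about the rest. With 25 per arm (section 16.0) and ten assignments known, an assumed number, a 5:5 split leaves 20:20. An 8:2 split leaves 17:23, so the best guess is right 23/40 = 57.5% of the time. This stands against any claim that other subjects are unblinded directly. It does not answer the concern that arm becomes linked with observed outcomes. Section 5.1 gives no block size, so how much more could be deduced is unknown.
- **Raters.** A reader might infer biased rating. The documents do not say who scores the CDR or ADAS-Cog or who reads MRI volumes, so this is a risk and not a demonstrated effect.

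On 9.2, a subject still followed has arguably not had a last visit. The two sections leave an ambiguity, not a contradiction. Committee approval is relevant to the ethics of telling subjects, but it does not supply the missing rules. The rationale in 33.2 requires that the subject be told; it does not require that the investigator be told.

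**Conclusion.** The point holds as a weakness in a stated rule. The blinded Principal Investigator is to learn and pass on the assignments of subjects who ask, at a visit that also collects endpoints, with no set order and no wait for subjects still in blinded follow-up. It should be corrected.

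The exposure is mainly to the month 36 to 60 data and to adverse event and conversion judgements. Its size cannot be computed, because enrolment dates, the number who ask and the identity of the raters are not given. The conclusion assumes some staggering of entry and at least one request before the last subject finishes. The documents do not support the stronger conclusions that endpoints have been biased or that the month-24 result is unsafe.

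**What to change.** Amend 6.5 and 33.1 together:

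1. An already unblinded person, the pharmacist or the research scientist, discloses directly to the subject.
2. Disclosure comes only after all assessments of that subject's final visit are completed and entered. That is Visit 15 for extension subjects, Visit 12 for those who decline the extension, and the last follow-up contact for withdrawn subjects still followed under 9.2.
3. The Principal Investigator and any raters are not told until the last month-60 record is locked, apart from the medical-need unblinding already in 6.5. Subjects are asked not to tell them.
4. Study completion is defined as subject-level or study-level. Disclosure dates are logged, and any later data from a disclosed subject are flagged.

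The cost is wording and a log, with no new staff. Subjects still obtain the information they need to enter other trials. They hear it from the pharmacist or research scientist instead of the investigator, and withdrawn subjects still in follow-up may hear later. Asking subjects for discretion cannot be enforced, so some leakage remains possible.
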